Both the PPI and control groups will have a sample size of 12 dyads (12 survivors and 12 caregivers; total 24 dyads). It is advised that pilot studies have a sample size $n=12$, as the standard error and 95% confidence interval narrow rapidly up until $n=12$ and then improvement levels off dramatically as samples increase⁴⁹. Using a Stata/14 software power analysis formula specific to our analysis of covariance approach, while assuming the Pearson correlation between the baseline and follow-up outcome is $r=0.70$, and using a two-sided comparison $\alpha = 0.027$ to allow for a Sankoh adjustment to the Hochberg procedure that assumes $r=0.50$ between the outcomes of the two comparisons, so that both multiple comparisons are sufficiently powered, this sample size provides 80% power to detect a 0.89 standard deviation (SD) mean difference between the PPI and control groups. This represents a large effect by Cohen’s criteria (small effect, 0.2 SD, medium, 0.5 SD, large, 0.8 SD difference)⁵⁰. Thus, if the PPI intervention has a large effect, this pilot study has sufficient statistical power to arrive at a confirmatory conclusion for Aim 1. Even if statistical significance is not achieved, if the study effect is in the expected direction, proof of concept will be demonstrated. Likewise, the study will provide estimates that

can be used in a sample size determination for a later larger study.

Aim 2: To determine if the PPI improves quality of interactions in couples during stressful discussion and collaborative problem-solving tasks we will analyze the dyadic tasks. Trained coders will code recordings using the Rapid Marital Interaction Coding System, v.2 (RMICS-2)^{51, 52}, a valid and reliable observational coding system for quantitative communication coding, using 6 hierarchical codes to describe dyadic behavior at a macro category level, focusing on positive and negative aspects of communication (e.g. laughter, hostility) and problem-solving. The unit of analysis is speaker turn and both spouses' communication is coded. This coding system allows for both verbal and nonverbal cues to be assessed. Audio/video data from the study will be downloaded and trained coders will assess for quality. Using Noldus Observer software, they will document how much time overall (total number of turns) each participant spent talking to his/her spouse/partner in each task and code these conversations using RMICS. Per standard guidelines⁵², 25% of audio will be assessed for reliability and drift between the 2 coders throughout the study using Cohen's kappa. Coders will be blind to which tapes are reliability coded, with kappa expected to be 0.6 for codes with adequate representation.

Coded data will be imported into SPSS for further analysis. Ratios of talk for each individual code will be created for both survivor and spouse (e.g. spouse problem discussion/total spouse talk). These ratios provide a more standardized measure for comparison and control for differences in how frequently participants speak (total talk). Coded communication will be analyzed using descriptive statistics to determine proportions of positive and negative talk. Given that these two variables represent a continuous score between 0 and 1 for each person, the pre to post comparison will be made with a paired sample t-test to test the Aim 2 *H2* hypothesis. A sample size of 24 couples provides 80% power to detect a 0.59 SD mean change from pre to post, which represents a medium-large effect size by Cohen's criteria. Realistically, we expect only a medium effect in the expected direction, so proof of concept will be demonstrated. Likewise, the study will provide estimates that can be used in a sample size determination for a later larger study.

Aim 3: To determine whether increases in mood in one partner are associated with improved mood in the other partner over time, we will analyze survivor and spouse PANAS scores using the Actor-Partner Interdependence Model (APIM) framework. In APIM models, the couple is the unit of analysis^{53, 54}. In this model, the predictor variables are a survivor's and spouse's positive and negative affect scores at weekly intervals. The outcome variables are a survivor and spouse's weekly affect. As seen in *Figure 2*, this analysis can determine the correlation between couples' scores at each time point (interdependence effects), so a specific growth-curve structure does not need to be specified. The model examines how one's own score predicts one's following week score (actor effects), and how one's weekly score predicts the following week's score of the other spouse (partner effects). These analyses are run simultaneously in a structural equation model with repeated measurements, using as many weeks as are available for each couple, so drop-outs are not an issue. The statistical power of Aim 3 is larger than Aims 1 or 2 because we have 8 repeated measurements. To determine the actual power, we would have to specify a value for the intraclass correlation coefficient (ICC) of the repeated measurements, and then apply a design effect. We suspect that even after doing that, however, we would only have sufficient

power to demonstrate feasibility. So, like Aims 1 and 2, Aim 3 will be a feasibility hypothesis.

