PPIs are typically targeted at the individual. However, due to the reciprocal nature of positive affect and positive close relationships (33), PPIs are ideally suited as a dyadic intervention. **In our innovative dyadic approach**, stroke survivors and caregivers complete PPIs each week on their own and together. Further, we are also examining **potential mechanisms of the dyadic PPI on couples' mood** through interactions and shared emotional processes. Research on emotion co-regulation supports the notion that mood states among family members are correlated (34). By having participants complete PPI activities on their own we expect that individual positive emotion will increase. Through PPI activities completed together, couples will share in positive experiences, thereby increasing positive affectivity and strengthening social bonds. Together, this can foster a more positive environment over time, and effect a synergistic change in positive affect and well-being for the dyad. Couples with greater well-being may be better emotionally equipped to handle the stresses of stroke, potentially reducing depressive symptoms (10, 12). Although our intervention is developed for and will be tested in local, community-dwelling couples post-stroke, it is developed so that it is easy to administer using telehealth where the intervention could benefit those geographically or situationally isolated.

Preliminary Data

With internal funding (University of Utah's Consortium for Family and Health Research (C-FAHR)), we have collected preliminary feasibility data on the proposed dyadic PPI (IRB_00080565). We developed the positive psychology activities booklet to be used in our PPI

protocol and sent it to 5 clinical, stroke survivor and caregiver stakeholders for readability, acceptability and applicability. We modified materials based on their feedback.

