Aim 1. To determine preliminary efficacy of the PPI in 24 couples with depressive symptoms in a randomized waitlist control pilot trial on mood and well-being. *H1a: The PPI will improve well-being and mood as assessed by established outcome measures in survivors and caregivers from pre- to post-intervention. H1b: Improvements in well-being and mood will be greater in the PPI vs. control group.*

Aim 2. To determine if the PPI improves quality of interactions in couples during stressful discussion and collaborative problem-solving tasks. *H2: The PPI will enhance the emotional tone of the couple’s interactions from pre- to post-intervention as measured by observational interaction coding.*

Exploratory Aim 3. To determine whether increases in mood in one partner leads to improvement in mood in the other partner over time as assessed by weekly self-report. *H3: Increases in mood in one partner will be positively associated with increase mood in*

the other partner and vice-versa; i.e. be synergistic across couples.

Study Population

Age of Participants: 18+, no upper limit

Sample Size:

At Utah: 70

All Centers:

Inclusion Criteria:

Inclusion criteria are:

- 1) Couples consisting of one partner who had an ischemic or hemorrhagic stroke ≥ 6 months ago and a cohabiting partner (living together ≥ 1 year) who self-identifies as the caregiver and is willing to enroll in the study.
- 2) Either one or both partner(s) report depressive symptoms as assessed by the PROMIS-Depression measure (no formal diagnosis is required).
- 3) Both partners must be community-dwelling adults age 18 years and older.
- 4) Both partners must be able to understand printed English instructions

Exclusion Criteria:

Exclusion criteria are:

- 1) Either partner does not consent to participate.
- 2) The caregiving partner has had a stroke or other major neurological condition.
- 3) Either partner is unable to understand printed English instructions.
- 4) Either partner has significant cognitive impairment (as assessed by the Telephone Interview for Cognitive Status, TICS).

Note: As this is a pilot study, we are restricting participation to only those who are able to understand printed English instructions and have mild/no cognitive impairment. We anticipate expanding inclusion criteria for future trials.

Design

Survey/Questionnaire Research

Prospective Clinical Research
Randomized
Phase I Clinical Trial
Other

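### The Aim 3 lagged actor-partner model, as described, has no stable person-level term, so lasting similarity between partners is mixed into the partner path that answers H3

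*Combined protocol and SAP*

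**What the plan says.** The statement of aims asks "whether increases in mood in one partner leads to improvement in mood in the other partner over time as assessed by weekly self-report", and H3 begins "Increases in mood in one partner will be positively associated with increase mood in" the other partner. Both are worded in terms of change over time.

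The Aim 3 paragraph under Statistical Methods, Data Analysis and Interpretation gives the model, an Actor-Partner Interdependence Model fitted to weekly PANAS scores as a structural equation model. Three kinds of term are described:

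- Actor paths: "The model examines how one's own score predicts one's following week score (actor effects".
- Partner paths: "how one's weekly score predicts the following week's score of the other spouse (partner effects".
- The correlation between the partners' "scores at each time point (interdependence effects".

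Because of that last term, the plan says, "so a specific growth-curve structure does not need to be specified". No random intercept, trait factor or centring on the person's own mean is described. The intraclass correlation (ICC) appears only in connection with a power calculation that was not carried out. The aim is labelled exploratory, and the paragraph ends by calling it a feasibility hypothesis.

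**The concern.** Weekly mood scores have two parts: a level that a person tends to keep, and movement around that level. H3 concerns the second. A lag-1 regression on undivided scores uses both. Last week's own score is an imperfect measure of a person's stable level. If partners' stable levels are alike, the other partner's score from last week therefore carries further information about that level, and it earns a non-zero coefficient even when neither partner influences the other. A same-week correlation does not remove this, because it links the partners within a week and does not carry a person's level from week to week.

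At stake is the reading of the partner path. The background presents shared emotional processes as a possible mechanism of the intervention, and this path is the trial's estimate of it. As described, the model cannot tell couples who are steadily happier or unhappier together from couples in whom mood passes from one partner to the other.

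**Working it through.** **Inputs from the documents.** 24 couples for analysis (Aim 1 sample size text) and weekly scores, "because we have 8 repeated measurements". Aim 3 states no power, effect size or correlation, so there is no figure to reproduce.

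**Assumed inputs, none given in the documents.** ICC is the stable share of the variance of weekly scores. rho is the correlation between partners' stable levels, omega the correlation between their weekly deviations, and phi the weekly carry-over of a deviation. Scores have variance 1.

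**Population partner path when the true partner effect is zero.**

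- Same-week correlation: r = ICC·rho + (1−ICC)·omega.
- Own lag-1 covariance: a = ICC + (1−ICC)·phi.
- Cross lag-1 covariance: c = ICC·rho + (1−ICC)·phi·omega.
- Partner path: (c − r·a)/(1 − r²) = ICC(1−ICC)(1−phi)(rho−omega)/(1−r²).

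The sign is that of rho − omega. The number of couples does not enter, so a larger sample would not remove the bias.

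**Numbers put in (ICC 0.5, phi 0.2, omega 0.2).** The numerator is 0.5 × 0.5 × 0.8 × (rho − 0.2).

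| rho | r | numerator | 1 − r² | path |
|---|---|---|---|---|
| 0 | 0.10 | −0.04 | 0.9900 | −0.04 |
| 0.2 | 0.20 | 0 | 0.9600 | 0 |
| 0.3 | 0.25 | 0.02 | 0.9375 | 0.02 |
| 0.5 | 0.35 | 0.06 | 0.8775 | 0.07 |
| 0.7 | 0.45 | 0.10 | 0.7975 | 0.13 |

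**Simulated rejection rates for the model as described** (24 couples, 8 weeks, week-specific means, paths equal over weeks, true partner effect zero, two-sided nominal 5%; ranges are across independent simulations):

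- rho 0.3: about 6–7% per path. This is almost no inflation, since the test rejects in about 6–7% even when rho equals omega.
- rho 0.5: 16–19% per path, and 30–32% of trials with either path significant (the upper figure at ICC 0.6).
- rho 0.7: 43–44% per path, and 64% for either.
- At rho 0.5 and 0.7, nearly all rejections are in the direction H3 predicts.

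**Varying omega with rho held at 0.5.** The per-path rate is 16–19% at omega 0.2, 11–13% at 0.3, 7–8% at 0.4 and about 6% at 0.5, where the bias is zero. At rho 0.3 and omega 0.5 the path is 0.5 × 0.5 × 0.8 × (−0.2)/(1 − 0.40²) = −0.04/0.84 = −0.05, and under 1% of paths are significant in H3's favour.

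**Standard errors are not the cause.** Couple-clustered standard errors leave the rate about the same (38% against 37% at ICC 0.5, rho 0.5, omega 0, phi 0.2), because the estimate itself is displaced.

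**With correlated random intercepts.** About 600 simulated trials per setting, fitted by maximum likelihood, with a joint two-degree-of-freedom test of both partner paths:

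| ICC, rho, omega, phi | without intercepts | with intercepts | mean path with intercepts |
|---|---|---|---|
| 0.6, 0.5, 0.2, 0.2 | 29.6% | 5.6% | 0.002 |
| 0.5, 0.5, 0, 0.2 | 50.7% | 5.0% | 0.001 |

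The spread of the partner-path estimate is then about 0.09, so a 95% interval extends about 1.96 × 0.09 = 0.18 on each side. Convergence matters at this sample size: under a different optimiser set-up the same test rejected in 16.7% and 7.1% of trials.

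**The case against.** Four arguments deserve weight.

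1. **The size and direction depend on rho minus omega, and the documents give neither.** This stands. A reader might infer that lasting similarity will show up as false support for H3. The documents do not support that: the bias vanishes when the two correlations are equal and reverses when omega is larger. Nor does the background remark that "mood states among family members are correlated" settle it. It is made in the context of emotion co-regulation and is at least as close to weekly co-movement (omega) as to stable similarity (rho).

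2. **Eligibility may lower rho.** Inclusion requires depressive symptoms in at least one partner, so couples with neither symptomatic are left out. Under bivariate normal mood, this would cut a correlation of 0.5 to 0.13 if half of individuals are symptomatic, or 0.29 if about 69% are; 0.7 would fall to 0.39 or 0.52. Selection is on PROMIS-Depression and the outcome is PANAS, so the actual reduction should be smaller. It does make the 43–44% case an upper illustration, not an expected rate.

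3. **The full specification may be in Figure 2.** That figure was not available, and waiving a growth-curve shape does not by itself rule out a random intercept. A reader might infer that the plan excludes any person-level term. The supportable statement is that the text describes none.

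4. **Aim 3 is exploratory, with no significance rule for H3.** This also stands. The rejection rates above use a conventional 5% test that the plan does not prescribe. The displacement of the estimate does not depend on any test, and an exploratory label does not remove it.

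**Conclusion.** The concern holds for the model as the text describes it. The partner path combines stable similarity between partners with week-to-week influence, and H3 asks about the latter. Under the assumed values with omega 0.2, the spurious path runs from −0.04 (rho 0) through 0 (rho 0.2) to 0.13 (rho 0.7), and per-path false positives run from near nominal to 43–44%. Which case applies cannot be judged from the documents, and the described model would not show it from the data either.

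The consequence is limited. A reader might infer that the trial's efficacy findings are affected. They are not: Aims 1 and 2 do not use this path, and Aim 3 is a feasibility hypothesis. What could go wrong is that a misleading mechanism estimate, in either direction, is carried into the design of later work. The change is worth making because it is cheap and uses data already being collected.

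**What to change.** In the Aim 3 paragraph, state that survivor and spouse each receive a random intercept, correlated between partners, so that actor and partner paths are estimated on weekly deviations from each person's own level. If Figure 2 already contains such terms, say so in the text. Hold the paths equal across weeks and fit positive and negative affect in separate models, so that the model is estimable with 24 couples. Base H3 on these partner paths, and report them with confidence intervals, apart from the stable between-partner correlation. Check convergence from more than one starting point.

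The cost is a few sentences in the plan and standard structural equation or multilevel code, with no new data. The downside is wider intervals for the partner paths, about 0.18 on each side in the settings simulated, so the trial is likely to give an imprecise estimate of partner influence. That suits an aim already described as one of feasibility.
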